3.8.1 Dietary guidance/restrictions

Beginning in the lead-in period, and continuing throughout the study, patients will be asked to follow instructions on medical nutrition in accordance with the American Diabetes Association (ADA) dietary guidelines or locally accepted guidelines. Patients will be provided with instructional material and training regarding the medical nutrition guidelines. Patients will be asked to follow a standard diabetic weight maintaining diet containing approximately 55% carbohydrate, 25% fat, and 20% protein. The total daily caloric intake for each patient will be limited to approximately 2000 kcal.

The timing and content of meals should remain consistent across the 7-day CGM system monitoring period. The timing and content of meals should be similar from the 7-day CGM testing at baseline vs. CGM testing during the treatment period to ensure comparability of data.

In order to keep the timing and content of meals consistent patients should avoid significant changes during 7-day CGM assessments (i.e., typical portion sizes, same pattern/meals when dining at restaurants, avoiding holidays/celebratory meals, etc).

Patients will be provided a standardized breakfast meal following guidelines at the study site on Day -7, Day 22, and Day 64. The standardized breakfast meal should account for approximately 35% of the daily calorie intake (~700 kcal). After the meal is given, only water will be provided through the completion of the meal test.

3.9 Discontinuation of investigational product

Patients MUST discontinue investigational product (and non-investigational product at the discretion of the Investigator) for any of the following reasons:

- Patient's request to stop study treatment;
- Any clinical adverse event, laboratory abnormality, or intercurrent illness which, in the opinion of the Investigator, indicates that continued participation in the study is not in the best interest of the patient;
- Pregnancy;
- Termination of the study by AstraZeneca;
- Loss of ability to freely provide consent through imprisonment or involuntary incarceration for treatment of either a psychiatric or physical (e.g., infectious disease) illness; or
- Unblinding a patient for any reason (emergency or non-emergency).

3.9.1 Discontinuation due to hyperglycemia (pre-specified glycemc parameters)

Discontinuation due to hyperglycemia during treatment

Patients will be instructed to perform fasting self-blood glucose monitoring (SBGM) during the study. Patients who have a fasting fingerstick glucose of ≥ 270 mg/dL (15 mmol/L) on 3 consecutive days will be instructed to call the Investigator site. The patient will be scheduled for a FPG performed by the central laboratory. If the FPG by central laboratory is ≥ 270 mg/dL or 15 mmol/L, the patient will be discontinued. If at the Day -7 visit, the patient has not been consistently performing fasting SBGM and his or her central laboratory FPG ≥ 270 mg/dL, the patient will be considered for discontinuation.

Table 1 Discontinuation criteria for patients who experience hyperglycemia during treatment

Discontinuation criteria by FPG during treatment	
At a site visit	FPG mg/dL (mmol/L)
Fingerstick (FPG)	≥ 270 mg/dL (15.0 mmol/L) for 3 consecutive days
Central laboratory (FPG)	≥ 270 (15.0 mmol/L), if has not performed FPG

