3.8 Restrictions

Patients are not permitted to use acetaminophen or paracetamol during the study, as these drugs may interfere with the CGM device.

Patients are to continue metformin XR during the study. Patients should discontinue other oral anti-hyperglycemic medications at least 4 weeks prior to Screening. The intent of this study is that patients do not deviate from their metformin regimen. However, in circumstances where a patient has a fasting glucose value above 270 mg/dL for 3 consecutive visits then the dose of metformin XR may be increased to the maximum dose of 2000 mg. This dose may be continued for the duration of the study. If such a situation occurs that patients are still not under 270 mg/dL fasting glucose after this increase in metformin XR dose then a decision to keep the patient in the study should be made only after consultation between the Investigator and the AstraZeneca clinical research physician. The decision should be documented by a note to the Investigator's file.

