3.9.2 Discontinuation due to elevated liver enzymes

The Investigator and the AstraZeneca representative will be notified by the central laboratory when any patient experiences elevation of liver enzymes AST $> 3 \times \text{ULN}$ (40 U/L for men and 72 U/L for women) and/or ALT $> 3 \times \text{ULN}$ (80 U/L for men and 72 U/L for women) and/or serum total bilirubin > 2.0 mg/dL. The study medication should be discontinued immediately and a repeat blood sample should be taken. Appropriate follow-up should be arranged for the patient.

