Note: Entry into the lead-in period (Day -28) should occur at least 7 days after Screening but no later than 14 days after receiving the Screening laboratory results. Study visits during the lead-in period and the double-blind treatment period should occur on the designated visit day ± 3 days.

- Screening can be performed over multiple visits. Entry into the lead-in period should occur at least 7 days after Screening and no later than 14 days after screening.
- If the patient discontinues during one of the 7 day CGM periods, remove CGM device. The CGM device should not remain in place longer than 10 days.
- Standard safety blood tests, urinalysis for safety analysis, and HbA1c will be performed 30 minutes prior to the standardized breakfast meal.
- A complete physical examination will be performed on days designated with an X. A brief physical examination will be performed on days designated with an X^d. See Section 5.2.2 for details.

- e. If patient is discontinuing the study due to an adverse event, a 5 mL blood sample for assessment of exenatide plasma concentration will be collected.
- f. See [Table 4](#) for a list of the safety laboratory variables for this study. Patients who discontinue should have a standard safety laboratory panel collected at the conclusion of their participation.
- g. Women of childbearing potential only.
- h. Glucose levels will be drawn 30 minutes before and just prior to breakfast and 30, 60, 120, and 180 minutes after breakfast. The post meal glucose tolerance test is provided in a 3 day window.
- i. Patients must be fasting at this time point.
- j. Includes hepatitis screen panel (anti-hepatitis C virus and HBsAg only).
- k. Patients should be instructed to perform fasting SBGM daily, and instructed to call the site if they have a FPG ≥ 270 mg/dL (15 mmol/L) for 3 consecutive days. The patient should have a FPG by central laboratory; if ≥ 270 mg/dL (15 mmol/L), the patient should be discontinued. If the patient has not performed fasting SBGM and the central laboratory FPG at Day -7 ≥ 270 mg/dL (15 mmol/L), the patient should be considered for discontinuation.

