5.2.6 Other safety assessments

5.2.6.1 Self-blood glucose monitoring

Patients will perform a fasting SBGM daily during the lead-in period. Fingersticks should be performed once daily after a minimum fast of 8 hours. If the FPG on 3 consecutive days is ≥ 270 mg/dL (15 mmol/L), the patient will be instructed to call the site. The site will review the glucose meter readings to confirm elevated glucose values. The patient will have a FPG performed by the central laboratory. If the FPG is ≥ 270 mg/dL (15 mmol/L), the patient will be considered for discontinuation from the study (see Section [3.9.1](#)). If at the Day -7 visit, the patient has not performed fasting SBGM consistently and the central laboratory FPG ≥ 270 mg/dL, the patient should be considered for discontinuation.

On the Day -8 visit, the site should review the patient's CGM data to ensure that the patient performed the calibration correctly and followed appropriate guidance to ensure recording of

CGM data. Patients who experience suspected symptoms of hypoglycemia should perform SBGM and document the glucose measurement/reading at the time of the symptoms.

Glucose meters will be provided locally and will display in units of either mg/dL or mmol/L, as is the customary standard of practice in that country. All glycemic discontinuation criteria have been provided for each unit of measure.

If fingerstick glucose values are discordant from glycemic control assessed by the central laboratory or with clinical symptoms, the patient's glucose meter should be tested and the procedure for using it reviewed with the patient.

Supplies will be provided to allow for approximately 100 blood glucose assessments per month for the duration of the study. Patients should bring their glucose meter with them at each study visit to assure that it is functioning properly. Patients may keep the glucose meters at the end of the study.

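### The hyperglycaemia rules in Sections 3.8, 3.9.1, 5.2.6.1 and 7.7 conflict, and the U/L figures in the liver-enzyme rule are coherent neither as ULN nor as 3 × ULN

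*Protocol*

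**What the plan says.** **Glucose.** Section 3.9.1 sends a patient with three consecutive days of fasting fingerstick at or above 270 mg/dL for a central-laboratory FPG. It then says: "If the FPG by central laboratory is ≥ 270 mg/dL or 15 mmol/L, the patient will be discontinued". Footnote k to Table 2 repeats the pathway: "The patient should have a FPG by central laboratory; if ≥ 270 mg/dL (15 mmol/L), the patient should be discontinued". Section 5.2.6.1 opens with "Patients will perform a fasting SBGM daily during the lead-in period", goes through the same steps and refers back to 3.9.1, but ends with "the patient will be considered for discontinuation from the study".

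Table 1, which belongs to Section 3.9.1, lists three days of fingersticks as a criterion in its own right. It counts the central-laboratory value only where the patient has not performed FPG.

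Section 3.8 says that if a patient "has a fasting glucose value above 270 mg/dL for 3 consecutive visits then the dose of metformin XR may be increased", up to 2000 mg, the higher dose may run to the end of the study. For a patient still not below 270 mg/dL after that, "a decision to keep the patient in the study should be made only after consultation between the Investigator" and the sponsor's research physician. Section 7.7 addresses the same background drug differently: a metformin XR change is for emergencies and may last up to 7 consecutive days, or 7 days within a month, before consultation is needed.

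**Liver enzymes.** Section 3.9.2 requires study medication to be stopped immediately when AST or ALT exceeds 3 × ULN (or bilirubin exceeds 2.0 mg/dL). The bracket after the AST multiple reads "40 U/L for men and 72 U/L for women) and/or ALT", and the ALT bracket gives 80 U/L for men and 72 U/L for women. The protocol states no ULN for either enzyme.

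**The concern.** These are instructions that sites must act on for individual patients. Where one section mandates removal, another asks for consideration and a third offers intensified background treatment, two sites can treat similar patients differently and each can cite the protocol. The liver rule calls for immediate action, yet the number that sets it off can be read in two ways.

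The trial's data are affected as well. CGM is worn only on Days -8 to -1, 21 to 28 and 63 to 70. A patient who leaves the study before Day 21 has no Week 4 or Week 10 CGM assessment; one who leaves between Days 28 and 63 has no Week 10 assessment. A patient who stays on more metformin XR contributes values on a changed background, because Section 8.5.1 puts all post-baseline measurements into the MMRM. How each site reads the rules therefore helps decide who is in the primary comparison and on what background therapy.

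**Working it through.** **1. The glucose rules side by side**

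| Place | Trigger | Action |
|---|---|---|
| 3.9.1 text | Fingerstick ≥270 mg/dL on 3 consecutive days, then central FPG ≥270 | Mandatory discontinuation |
| Table 1 | Fingerstick ≥270 on 3 consecutive days; or central FPG ≥270 if FPG not performed | Listed as discontinuation criteria |
| Table 2, footnote k | As 3.9.1 text | Should be discontinued |
| 5.2.6.1 | As 3.9.1 text | Considered for discontinuation from the study |
| 3.8 | Fasting value >270 at 3 consecutive visits | Metformin XR may be increased for the rest of the study; possible retention after consultation |
| 7.7 | Emergency | Metformin XR change for up to 7 days before consultation |

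The units are not the problem: 270 / 18 = 15.0 mmol/L, using the usual conversion factor of 18 as an assumption. The conflict lies in the action and in the need for confirmation.

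**2. Can one patient meet both 3.8 and 3.9.1?** On-treatment laboratory FPG is scheduled on Days 1, 15, 22, 57, 64 and 70. Three consecutive visits span:

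- Days 1, 15, 22: 22 − 1 = 21 days
- Days 15, 22, 57: 57 − 15 = 42 days
- Days 22, 57, 64: 64 − 22 = 42 days
- Days 57, 64, 70: 70 − 57 = 13 days

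The 3.8 trigger therefore takes 13 to 42 nominal days. The 3.9.1 trigger takes 3 days plus one laboratory result. A patient who stays above 270 mg/dL and self-monitors daily meets 3.9.1 first and should have left before 3.8 could apply; if still in the study, the patient meets both. One section then mandates removal and the other permits retention, and nothing says which prevails.

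**3. Does the study period separate the rules?** Section 5.2.6.1 opens with the lead-in, and 3.9.1 has a sub-heading for the treatment period. But the 3.9.1 text has patients self-monitor during the study and includes a Day -7 provision. Footnote k belongs to a row with visits on Days -8, -1, 21 and 63. Section 5.2.6.1 itself cites 3.9.1. The split by period is not carried through.

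**4. The liver figures**

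| | Bracketed figure (U/L) | If it is 3 × ULN: implied ULN = figure / 3 | If it is ULN: trigger = 3 × figure |
|---|---|---|---|
| AST, men | 40 | 13.3 | 120 |
| AST, women | 72 | 24.0 | 216 |
| ALT, men | 80 | 26.7 | 240 |
| ALT, women | 72 | 24.0 | 216 |

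The men-to-women ratio does not depend on the reading: 40 / 72 = 0.56 for AST and 80 / 72 = 1.11 for ALT. The sexes are ordered one way for AST and the other way for ALT, and the men's AST figure is half the men's ALT figure. A man's AST of 60 U/L is above the trigger on one reading (40) and well below it on the other (120). Appendix D does not settle this: it refers to Section 6.3.7 for managing liver abnormalities, and 6.3.7 refers back to Appendix D.

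**The case against.** **Different triggers.** A reader might infer that one and the same fasting glucose leads to three different actions. The text does not go that far. Section 3.8 needs values above 270 mg/dL at three visits; 3.9.1 needs values at or above 270 on three days plus a laboratory result. A patient can meet 3.8 without meeting 3.9.1. This stands, and it confines the direct clash between those two sections to patients who meet both.

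**Lead-in scope.** Section 5.2.6.1 can be read as a lead-in rule about leaving the study, while 3.9.1 sits under discontinuation of investigational product. This weakens the contrast between considered and mandatory but does not remove it, given the cross-reference and footnote k.

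**Liver figures.** A reader might infer that the four figures cannot all be 3 × ULN. Without a stated ULN that cannot be proved. Three of the four imply ULNs of 24 to 27 U/L, so a single misprint in the men's AST is possible. The multiple itself is clear and matches exclusion criterion 29, and the central laboratory issues the alert. All of this stands. Even so, the text never says whether the multiple or the printed figure governs, and a misprint in an immediate-stop rule still needs correcting.

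**Effect on the result.** If the worst-controlled patients are mostly on placebo, losing them or raising their metformin would narrow the treatment difference, not inflate it. The plan allows for 30% dropout, and the MMRM keeps Week 4 and early-termination data. The direction is plausible under that assumption. The dropout allowance protects power, however; it does not protect against selective loss or unequal background therapy.

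**Conclusion.** Wrong as written. The discontinuation rules cannot all be followed together. The mandatory wording of 3.9.1 and footnote k does not match 5.2.6.1. Table 1 does not match its own section on laboratory confirmation. Sections 3.8 and 7.7 set different limits on metformin XR changes. No precedence is stated for a patient who meets both 3.8 and 3.9.1. The figures in 3.9.2 do not say whether they are ULN or 3 × ULN and are not coherent either way; the men's AST trigger alone reads as 40 or 120 U/L, a threefold range.

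The case for change rests on patient safety and uniform conduct across sites. A reader might go further and put a mg/dL bias on the primary difference. The document does not support that: it does not say how many patients would reach these limits, in which arm, or how far their change from baseline would differ from the rest. Section 3.8 can also raise the dose only for patients below 2000 mg. The size of the effect on the primary comparison is unknown, and the finding does not depend on it.

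**What to change.** The sponsor's clinical team should reconcile Sections 3.8, 3.9.1 with Table 1, Table 2 footnote k, 5.2.6.1 and 7.7 into one hyperglycaemia rule. It should state the measurement that counts, whether laboratory confirmation is needed, the period it covers (lead-in or treatment), whether the patient leaves product or study, and which provision takes precedence. The team should also reconcile the figures in 3.9.2 with the stated ULN multiple and label them as ULN or as 3 × ULN. No view is taken here on which rule, dose or threshold is right.

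The cost is amendment wording and a letter to sites. No new data collection is needed: Sections 3.11, 7.5 and 7.7 already require reasons for discontinuation, drug administration and regimen changes to be documented or reported. Whether to examine CGM data collected after a metformin XR increase separately is a matter for the SAP and not a condition of this fix.

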3.9.1.1 Discontinuation due to hypoglycemia or symptoms suggestive of hypoglycemia

Blinded study medication or open-label metformin XR should not be down-titrated and patients should not be discontinued from any treatment phase based on single episodes of hypoglycemia or symptoms of hypoglycemia unless clinically indicated. The assessment of a single fingerstick or central laboratory glucose value should not be the sole assessment used to determine patient discontinuation due to hypoglycemia. Clinical indications for discontinuation due to hypoglycemia may include the following:

- Symptoms suggestive of hypoglycemia (e.g., sweating, shakiness, increased heart rate, confusion, dizziness, lightheadedness, or hunger) in the absence of environmental factors known to contribute to hypoglycemia (i.e., excess physical activity, concurrent illness, or missed or delayed meal) and/or
- Documented fingerstick plasma glucose values ≤ 50 mg/dL (2.8 mmol/L) on multiple occasions (2 or more occasions).

A patient may also be discontinued from the study due to severe hypoglycemia as determined by the Investigator. **No down-titration of blinded study medication or metformin XR will be allowed at any time during the study except in cases noted in Section 7.7.**

If fingerstick glucose values are discordant from glycemc control assessed by the central laboratory or with clinical symptoms, the patient's glucose meter should be tested and the procedure for using it reviewed with the patient.

3.9.1.2 Discontinuation due to elevated serum creatinine

During the lead-in period, patients with a Scr ≥ 1.5 mg/dL (132.6 $\mu\text{mol/L}$) in males or ≥ 1.4 mg/dL (123.8 $\mu\text{mol/L}$) in females will be discontinued from the study.

- During the double-blind treatment period, patients with a Scr ≥ 1.5 mg/dL (132.6 $\mu\text{mol/L}$) but < 2.0 mg/dL (176 $\mu\text{mol/L}$) in males or ≥ 1.4 mg/dL (123.8 $\mu\text{mol/L}$) but < 2.0 mg/dL (176 $\mu\text{mol/L}$) in females, will have their open-label metformin XR held and a confirmatory repeat Scr drawn within 1 week. If the repeat Scr is ≥ 1.5 mg/dL (132.6 $\mu\text{mol/L}$) in males or ≥ 1.4 mg/dL (123.8 $\mu\text{mol/L}$) in females, the patient must be immediately discontinued from the study, AstraZeneca notified, and an early discontinuation visit performed which will include samples for the assessment of plasma concentrations. If the repeat Scr is < 1.5 mg/dL (males) or < 1.4 mg/dL (females), study medication may be resumed unless otherwise contraindicated.
- During the double-blind treatment period, patients (males and females) with a Scr ≥ 2.0 mg/dL (176 $\mu\text{mol/L}$), will have both blinded study medication and open-label metformin XR held and a confirmatory repeat Scr drawn within 1 week. If the repeat Scr is ≥ 1.5 mg/dL (132.6 $\mu\text{mol/L}$) in males or ≥ 1.4 mg/dL (123.8 $\mu\text{mol/L}$) in females, the patient must be immediately discontinued from the study, AstraZeneca notified, and an early discontinuation visit performed which will include samples for plasma concentrations. If the repeat Scr is < 1.5 mg/dL (males) or < 1.4 mg/dL (females), study medication may be resumed unless otherwise contraindicated.

3.9.2 Discontinuation due to elevated liver enzymes

The Investigator and the AstraZeneca representative will be notified by the central laboratory when any patient experiences elevation of liver enzymes AST $> 3 \times \text{ULN}$ (40 U/L for men and 72 U/L for women) and/or ALT $> 3 \times \text{ULN}$ (80 U/L for men and 72 U/L for women) and/or serum total bilirubin > 2.0 mg/dL. The study medication should be discontinued immediately and a repeat blood sample should be taken. Appropriate follow-up should be arranged for the patient.

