15. Repeated intermittent thyroid replacement treatment (patients receiving stable doses of thyroid replacement for a minimum of 2 months prior to Screening may be enrolled);

16. Repeated intermittent anti-hypertensive agent treatment (patients receiving stable doses of anti-hypertensive for a minimum of 2 months prior to Screening may be enrolled);
17. Repeated intermittent anti-depressant treatment (patients receiving stable doses of antidepressants for a minimum of 2 months prior to Screening may be enrolled);
18. History of unstable or rapidly progressing renal disease, or severe renal impairment (creatinine clearance <30 mL/min);
19. History of alcohol or drug abuse within the previous 1 year;
20. Unstable major psychiatric disorders, as determined per the Investigator's discretion;
21. Immunocompromised individuals such as patients who have undergone organ transplantation or patients diagnosed with human immunodeficiency virus;
22. History of hemoglobinopathies (sickle cell anemia or thalassemias, sideroblastic anemia);
23. Donation of blood or plasma to a blood bank within 3 months of Screening;
24. Administration of any other investigational drug or participation in a clinical research trial within 30 days of planned enrollment to this study;
25. History of acute pancreatitis associated or not with using an anti-diabetic drug therapy;
26. Has severe gastrointestinal disease, including gastroparesis;
27. Has acute or chronic hepatic impairment;
28. Has any condition which in the Investigator's opinion may render the patient unable to complete the study or which may pose significant risk to the patient;
29. Active liver disease and/or significant abnormal liver function defined as aspartate aminotransferase (AST) >3 × upper limit of normal (ULN) and/or alanine aminotransferase (ALT) >3 × ULN and/or serum total bilirubin >2.0 mg/dL;
30. History of positive serologic evidence of current infectious liver disease including anti-HAV (IgM), HbsAg, or anti-HCV. Subjects who may have isolated positive anti-HBs may be included;
31. Personal history or family history of medullary thyroid carcinoma or inpatients with multiple endocrine neoplasia syndrome;

32. Serum creatinine (Scr) ≥ 1.5 mg/dL (132.6 $\mu\text{mol/L}$) for males and ≥ 1.4 mg/dL (123.8 $\mu\text{mol/L}$) for females;
33. Creatine kinase $\geq 3 \times$ ULN;
34. Anemia of any etiology, defined as hemoglobin ≤ 12.0 g/dL (120 g/L) for men and hemoglobin ≤ 11.0 g/dL (110 g/L) for women;

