4.2 Treatment period

During the double-blind treatment period, patients will be instructed to take either EQW + open-label metformin XR (1500-2000 mg) OR placebo + open-label metformin XR (1500-2000 mg) once weekly (Day 7 each week). Patients will continue to take metformin XR once daily with the evening meal.

4.2.1 Randomization, Day 1, Visit 6

Patients are to arrive at their study visit on Day 1. Study procedures will be performed as listed in [Table 2](#). The IVRS/IWRS should be notified if the patient is discontinued from the study.

The patient's eligibility for randomization will be confirmed (see [Inclusion criteria](#) Section 3.1 and [Exclusion criteria](#) Section 3.2). The data from the CGM device from the 7-day CGM period during the lead-in will be reviewed for compliance. A 70% compliance rate is required to randomize the patient.

Samples will be taken from patients for FPG, HbA1c, and safety laboratory assessments. See [Table 4](#) for a list of the safety laboratory variables.

At the conclusion of the Day 1 visit, the patient will be randomized via IVRS/IWRS, and the double-blind study drugs (EQW or placebo) will be assigned and dispensed.

Patients will take their first dose of double-blind study medication at the site. The time of first dose will be noted on the eCRF. Patients will be trained on IP administration at this visit.

Patients will take their open-label metformin XR with the evening meal.

Patients will remain at the study site for collection of pharmacokinetic (PK) and biomarker blood samples according to the sampling described below:

- Perform PK blood sampling (see Section 5.4).
- Collect blood samples for biomarker analysis (see Section 5.7).

Prior to leaving the study site at the end of visit on Day 1, the patient will be scheduled for a Day 15 visit.

In addition, patients will be reminded:

- Of the fasting requirements for the Day 15 visit (at least 8 hours prior to visit).
- To call the investigative site if the fasting daily glucose on 3 consecutive days is ≥ 270 mg/dL (15 mmol/L).
- To bring study medication and glucose meter to the next scheduled study visit.
- To abstain from tobacco, nicotine or nicotine replacement, alcohol, and caffeine for 24 hours prior to and during the study visits, which include the 24-hour glucose monitoring period.
- To refrain from strenuous exercise, contact sports, and sunbathing for the 24 hours prior to all study site visits.

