5.2 Safety assessments

5.2.1 Laboratory safety assessments

Standard clinical laboratory tests, blood pressures and heart rate will be taken at the times indicated in the Study Plan (see [Table 2](#))

[Table 4](#) presents the laboratory safety variables measured for this study.

Table 4 Laboratory safety variables

Hematology	Clinical Chemistry (serum)
Hemoglobin	Creatine kinase (creatine phosphokinase) (CK) (CPK)
Hematocrit	Total bilirubin
Red blood cell count	Alkaline phosphatase (ALP)
White blood cell count and differential	Aspartate transaminase (AST, SGOT)
Platelet count	Alanine transaminase (ALT, SGPT)
	Amylase
	Lipase
Urinalysis	Total protein albumin
pH, protein, glucose, leukocyte esterase, blood by dipstick	Electrolytes – sodium, potassium, chloride
Microscopy if dipstick positive for blood, leukocyte esterase or protein	Serum creatinine (Scr), calculated creatinine clearance (Cockroft-Gault formula)
Urine HCG pregnancy test for WOCBP (HCG minimum sensitivity of 25 IU/L)*	Blood urea nitrogen (BUN)

*Note: If a urine HCG test is positive, a blood specimen will be obtained and a serum pregnancy test will be performed by the central laboratory for confirmation.

Additionally, a serum beta-HCG pregnancy test will be performed if necessary.

The Investigator should make an assessment of the available results with regard to clinically relevant abnormalities. The laboratory results should be signed and dated and retained at center as source data for laboratory variables. For information on how adverse events based on laboratory tests should be recorded and reported, see Section 6.3.

In case a patient shows an AST or ALT $\geq 3 \times$ ULN or total bilirubin $\geq 2 \times$ ULN please refer to [Appendix D](#) ‘Actions required in cases of combined increase of Aminotransferase and Total Bilirubin – Hy’s Law’, for further instructions.

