6.3.7 Hy’s Law

Cases where a patient shows an AST or ALT $\geq 3 \times$ ULN or total bilirubin $\geq 2 \times$ ULN may need to be reported as SAEs. Please refer to [Appendix D](#) for further instruction in cases of combined increase of aminotransferase and total bilirubin.

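### Section 3.9.2 sets an immediate liver stop at AST or ALT >3 × ULN but prints unlabelled, irregular U/L figures beside it, so the stop level can be read two ways that differ threefold

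*Protocol*

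**What the plan says.** Section 3.9.2 has the central laboratory notify the investigator and the sponsor when AST or ALT is above 3 × ULN, or total bilirubin is above 2.0 mg/dL. Each enzyme criterion is followed by a parenthesis in U/L by sex. For AST it reads "40 U/L for men and 72 U/L for women) and/or ALT". For ALT it reads "80 U/L for men and 72 U/L for women) and/or serum total bilirubin". The action is: "The study medication should be discontinued immediately and a repeat blood sample should be taken". Follow-up is then arranged. The section states no route back to treatment.

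Other places use the multiple without any U/L figure:

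- Exclusion criterion 29 in Section 3.2: "significant abnormal liver function defined as aspartate aminotransferase (AST) >3 × upper limit of normal (ULN", with the same multiple for ALT and the same bilirubin limit.
- Section 5.2.1, in the sentence that begins "In case a patient shows an AST or ALT", uses ≥3 × ULN and sends the reader to Appendix D.
- Section 6.3.7 uses ≥3 × ULN for possible SAE reporting and points to Appendix D "for further instruction in cases of combined increase of aminotransferase and total bilirubin".
- Appendix D, Sections 2 and 3, use ≥3 × ULN for Hy's Law definitions and alerts.

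Appendix D Section 1 names 6.3.7 as the place for liver management guidance.

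**The concern.** A stopping limit should be one number per patient. Here the criterion is a multiple of a quantity the protocol never gives, followed by figures that could be either that quantity or the multiple itself. The two readings lead to different actions on the same result, and the action is an immediate stop. The creatinine rule in 3.9.1.2 says that after a satisfactory repeat value "study medication may be resumed unless otherwise contraindicated"; 3.9.2 has no matching sentence, so its text does not reverse a stop made on the wrong reading. On one reading a patient may lose treatment needlessly; on the other, the specified stop may come late.

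The rule is used often. AST and ALT are in the safety panel (Table 4), which Table 2 schedules on Days 1, 15, 22, 57, 64 and 70.

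The figures also do not look like one coherent set, so a slip in at least one of them is a reasonable suspicion.

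**Working it through.** **Inputs**, all from Section 3.9.2: multiple 3; AST 40 (men), 72 (women); ALT 80 (men), 72 (women), in U/L. The protocol gives no AST or ALT reference range, so the figures cannot be reproduced from anything else in it.

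**Step 1: two readings.** Reading A takes each figure as the limit, so implied ULN = figure / 3. Reading B takes each figure as the ULN, so limit = 3 × figure.

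| | Printed | A: stop above | A: implied ULN | B: stop above |
|---|---|---|---|---|
| AST men | 40 | 40 | 40/3 = 13.3 | 3 × 40 = 120 |
| AST women | 72 | 72 | 72/3 = 24.0 | 3 × 72 = 216 |
| ALT men | 80 | 80 | 80/3 = 26.7 | 3 × 80 = 240 |
| ALT women | 72 | 72 | 72/3 = 24.0 | 3 × 72 = 216 |

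The stop levels differ by a factor of 3 in every row.

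**Step 2: what this does to a patient.** A man with AST 60 is stopped under A (60 > 40) and continues under B (60 < 120). A woman with AST or ALT 150 is stopped under A (150 > 72) and continues under B (150 < 216).

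**Step 3: a third course.** One may ignore the figures and use the laboratory's own ULN. Its value is not in the protocol. If it is assumed to lie between 30 and 45 U/L, the limit is 3 × 30 = 90 to 3 × 45 = 135 U/L. The man at 60 then continues and the woman at 150 is stopped, which matches neither A nor B for both patients. The ambiguity itself does not depend on this assumption.

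**Step 4: coherence of the set.** These ratios are the same under A and B.

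- Men to women: AST 40/72 = 0.56; ALT 80/72 = 1.11. The sex order reverses.
- AST to ALT: men 40/80 = 0.50; women 72/72 = 1.00.

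Three figures lie close together (72, 72, 80; the largest is 80/72 = 1.11 times the smallest). Male AST stands apart, at 0.50 to 0.56 of the others, which is why it is the most suspect. That is an inference from the pattern; the ratios alone do not prove which figure is wrong.

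**Step 5: search for a tie-breaker.** Exclusion 29, Sections 5.2.1 and 6.3.7, and Appendix D all give the multiple only. None supplies a U/L limit or a ULN.

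**The case against.** The best defence is that the multiple is the rule and the figures are a gloss. Every other liver threshold uses the multiple, notification comes from the central laboratory, and sites are not asked to derive a limit. This makes 3 × the laboratory's ULN the natural operative rule, and it makes disagreement between sites speculative. It does not remove the defect: 3.9.2 still prints figures that a laboratory could program or an investigator could apply.

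Several stronger readings are tempting and should not be drawn:

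- *The figures contradict the multiple.* Not shown. Read as ULNs, all four are formally compatible with it; read as limits, 72 is exactly 3 × 24. A misfit could be proved only with outside reference ranges. The text is also machine-read from PDF, which calls for some caution about single digits.
- *An eligible man could meet the 40 U/L stop on his Day 1 sample, the day of his first dose (Section 4.2.1: "Patients will take their first dose of double-blind study medication at the site").* This applies Reading A to stopping and another ULN to eligibility. Under A, exclusion 29 would also cut at 40, so the case needs a rise after screening.
- *Women stay on drug until 216 U/L.* Section 3.9 separately requires a stop for any laboratory abnormality that the investigator judges makes continuing unwise, and Appendix D requires a data review at ≥3 × ULN. Nor can 216 be expressed as a larger multiple of some other ULN without mixing readings; under B it is exactly three times.
- *The > in 3.9.2 against ≥ elsewhere is an error.* The ≥ sections govern Hy's Law review and reporting, a different action. The > in 3.9.2 agrees with exclusion 29.

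**Conclusion.** The point holds as a drafting defect in a safety rule. Section 3.9.2 fixes an immediate stop with unlabelled figures, and the stop level is either AST 40/72 and ALT 80/72 U/L or AST 120/216 and ALT 240/216 U/L (men/women). The set is irregular across sex and enzyme, at least one figure is suspect, and the protocol offers nothing to resolve it. It should be corrected, since it is a decision threshold for patients on treatment.

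The conclusion rests only on the printed figures and on the absence of a reference range. The documents do not show how many patients would fall between the two limits, so no count is given. The rule is identical in both blinded arms, and a reader should not infer bias between arms or any effect on power or alpha.

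A clerical matter sits beside it: Appendix D Section 1 cites 6.3.7, which refers back to Appendix D. Section 3.9.2, the only section with a liver-specific stopping action, is the likely intended target, though the text does not say so.

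**What to change.** In Section 3.9.2 delete both parentheses and write: *AST >3 × ULN and/or ALT >3 × ULN (central laboratory sex-specific reference range) and/or serum total bilirubin >2.0 mg/dL*. Keep the > sign; changing it to ≥ would make a patient at exactly 3 × ULN eligible under exclusion 29 and yet subject to the stop. If figures are wanted, print the ULN and the limit for each enzyme and sex as separate, labelled numbers taken from the laboratory.

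Confirm that the central laboratory alert is set to the same limits. As a clerical correction, point Appendix D Section 1 to 3.9.2 if that is what was meant.

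The cost is one sentence, one cross-reference and a check of the alert settings. No visit, sample or analysis changes.
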